## 1.5 Need for a pilot safety trial

A pilot clinical trial will be conducted with approximately 100 healthy adult volunteers, to assess the safety and tolerability of the ancientbiotic product on human skin. We want to find out whether, after completion of laboratory tests to human cells, there is any suspicion that the ancientbiotic causes inflammation to human cells. We consider this highly unlikely given (1) the data from cytotoxicity, irritation and wound healing assays cited above; and (2) that the product consists entirely of edible household ingredients.

**Study Design:** non-randomised, uncontrolled, Phase I pilot trial.

**Participants:** Adults aged 18-79 years, community-dwelling, male or female, without a diagnosis of diabetes, immune-related disease (asthma, eczema, psoriasis), pregnancy, or recent infection will be recruited. People with known dietary allergies will be excluded. People with Covid-19 infection, Covid-19 symptoms, or who are self-isolating due to Covid-19 exposure, will be excluded.

**Intervention:** Sticking plaster infused with one drop of the liquid Bald's salve ancientbiotic compound, applied to the skin of the upper arm, worn for 48 hours.

**Outcomes:** Adverse skin effects over 48 hours e.g. redness, heat, swelling or other. Type, number (%) and spread/distribution will be recorded. Digital photographs will be taken of any suspected skin reaction.

## 1.6 Ethical considerations

The trial will be conducted in full conformance with the principles of the Declaration of Helsinki and Good Clinical Practice (GCP) guidelines. It will also comply with all applicable UK legislation and University of Warwick Standard Operating Procedures (SOPs). All data will be stored securely and held in accordance with the General Data Protection Regulation.

Before enrolling people into the study, we will ensure that we have the approval of the Research Ethics Committee (REC). We will not be permitted to enrol people into the trial until written favourable opinion is received from the REC. The sponsor for the trial is the University of Warwick.

The study team will ensure that participants' anonymity is maintained. Participant identifiable information will be stored securely on an electronic database. The consent form will hold participant identifiable information, including name, mobile or home telephone number and email address. We will not hold any other identifiable information and will not access any medical records. Data will be stored securely and separately from other forms that are pseudo-anonymised, thus only labelled with a unique trial ID number. All documents will be stored securely and will only be accessed by study staff and authorised personnel. The study will comply with relevant UK data protection legislation, which requires data to be pseudo-anonymised as soon as it is practical to do so.

Data will be collected at baseline and follow-up assessment after 48 hours, and then entered directly into a secure database developed by WCTU. Paper forms will be on site at WCTU under locked conditions for the duration of the study; these will be considered source documents for the study. Email contact with the research team will be stored on the WCTU M drive server and held for the purposes of data checking and for monitoring purposes only. Direct access to source data and documents will be granted to authorised representatives from the sponsor, host institutions and the regulatory authorities to permit trial related monitoring, audits and inspections.

We expect all approaches from potential volunteers will be made to the study team directly. We will not apply to access any medical or social care data. We seek signed consent from participants to provide the study team with their personal contact details (telephone number and email) and consent for a photographic image to be taken of the patch test area should any events occur. Participants will be provided with a study email address and telephone number to contact the team straight away for advice.

All participants will be contacted by phone or email after 48 hours and a photo taken of the affected area where any suspected adverse event has occurred. Photographs from a small sample of volunteers with no skin reaction (n=5) will be taken for control purposes only.

Participants who are not fluent in written English will be excluded from the study as we do not have capacity for translation at this stage in the research process. We will exclude adults lacking capacity to consent.

## **1.7 CONSORT**

The trial will be reported in line with the CONSORT (Consolidated Standards of Reporting Trials) statement (Lancet 2001, **357**: 1191-1194).

## **1.8 Assessment and management of risk**

There will be some risk of experiencing skin redness or irritation from the skin patch test, arising either from application of the Bald's salve or from the sticking plaster. The products within the salve include garlic (active ingredient allicin), onion, wine and bovine bile. We do not anticipate any serious adverse events such as those resulting in death, hospitalisation, life threatening illness or permanent disability. Any participant experiencing any discomfort will be advised to remove the plaster and gently wash the area with soap and water. If symptoms persists, we advise them to visit their GP.

In light of Covid-19, there are also risks associated with contact between participants and the research team. We have taken steps to ensure rules regarding distancing and protection are adhered to. A Perspex sheet will be placed between the attending volunteer and researcher; facial masks will be worn by all personnel and participants. The Perspex sheet will be adapted to allow the participant's upper arm to be accessed for patch test application. Face to face assessment at 48 hours, as originally planned, has been replaced with telephone or video link contact. The study will be administered in keeping with WCTU SOPs for risk assessment and monitoring.

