## 2.8 Consent

**Confirmation of eligibility, and participant approach:**

1. Volunteer contacts the study team expressing interest in the study.
2. Trial team undertake eligibility screening and volunteer provided with Participant Information Sheet (PIS).
3. Allowed 48 hours to consider participation and ask any questions they may have.
4. Potential participant contacted by email, or phone by a member of the research team.
5. Signed consent obtained via post or at clinic.

**Informed consent:** volunteers will be invited to a clinic appointment where consent will be taken in person by an appropriately trained member of the clinical or research team.

**Adults lacking capacity:** will be excluded from the study.

**GP notification:** We do not intend to inform the participant's GP. It will be up to each participant to inform their own GP that they are taking part in the study. We recommend that anyone experiencing signs of persistent skin irritation, lasting after washing/ beyond 48 hours, should contact their GP.

**Timing of consent:** Written informed consent will be obtained by a suitably trained member of the research team (FH/JB) at the Warwick Medical School, after allowing sufficient time for the potential

participant to consider their decision and ask questions about the study. Sufficient time for some potential participants may result in a decision to take part in the trial immediately after receiving all the relevant information. Alternatively, if potential participants would like to leave with the information and decide later, they will be free to do so, and can contact the research team at a later time.

**New information:** We do not anticipate any new information arising that may affect participants' willingness to take part in the study. We will stagger administration initially. If any significant adverse events arise in the first 10 participants, then the study will be halted and the sponsor informed immediately. If minor skin reaction or no reactions occur over 48 hours for the first 10 volunteers, we will continue to roll out administration to the remaining volunteers.

**Decline/withdrawal:** Participants will have the option to withdraw before treatment starts, if for any reason they change their mind. The participant will remain free to withdraw at any time without giving reasons.

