# 3 METHODS AND ASSESSMENTS

## 3.1 Schedule of data collection

**Table 1. Trial visits/assessments**

Visit	WMS Clinic / Phone	WMS Clinic	WMS Clinic
Time-point	Pre-consent	Day 0	Day 2
Eligibility checks (in person or on phone)	X		
Written/verbal information about study	X		
Written informed consent	X	X	
Digital photograph image, if indicated			X
Skin check at baseline		X	
Outcome assessment			X
Any other adverse event		X	X

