## 3.2 ADVERSE EVENT MANAGEMENT

### 3.3 Definitions

#### 3.3.1 Adverse Events (AE)

An Adverse Event (AE) is defined as any untoward medical occurrence involving a participant, which does not necessarily have a causal relationship with the intervention or trial.

**Expected AEs**, related to the ancientbiotic intervention, may include:

- Skin redness
- Skin itchiness
- Skin discomfort

We will capture symptoms arising within and at 48 hours.

**Unexpected AEs** related to the ancientbiotic will be recorded via self-report by the participant up to 48 hours or at 48 hours when contacted by the research team.

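### Reactions that make a volunteer remove the plaster early are documented at the 48-hour contact, not at removal, so their character and spread may rest on recall

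*Protocol*

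**What the plan says.** **Early removal.** Protocol section 1.8 states: "Any participant experiencing any discomfort will be advised to remove the plaster and gently wash the area with soap and water". It continues: "If symptoms persists, we advise them to visit their GP". Section 2.8, under GP notification, adds: "We recommend that anyone experiencing signs of persistent skin irritation, lasting after washing/ beyond 48 hours, should contact their GP". None of these sentences mentions telling the study.

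**Contact route.** Section 1.6 provides one: "Participants will be provided with a study email address and telephone number to contact the team straight away for advice". Section 3.3.1 says that symptoms within the 48 hours, as well as at 48 hours, are captured. It also says that unexpected events are "recorded via self-report by the participant up to 48 hours or at 48 hours when contacted by the research team".

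**Image and assessment.** In section 1.6 all participants are to be "contacted by phone or email after 48 hours and a photo taken of the affected area where any suspected adverse event has occurred". Section 2.2 likewise puts the request for an image after 48 hours. In Table 1 (section 3.1) the row "Digital photograph image, if indicated" and the outcome-assessment row are marked at Day 2 only. Section 1.5 promises photographs of any suspected reaction but gives no time.

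**Outcome.** Section 2.4.1 makes both the frequency and the character of adverse events the primary outcome. Sections 1.5 and 5.1 add type, number and spread.

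**The concern.** The plan expects some volunteers to end exposure before 48 hours, and expects this because they have a reaction. Yet the only scheduled visual record is set by the calendar and not by the end of exposure. The volunteers whose reaction made them stop are then seen on skin that has been washed and has had time to recover. Those who wear the plaster to the end can be seen soon after it comes off.

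Time since exposure thus differs systematically between the two groups, and the gap is longest for those who stopped soonest. The trial is uncontrolled and unblinded, and face-to-face assessment has been replaced by remote contact. A photograph or video call is therefore the only visual evidence beyond what the volunteer says. At stake is how well the plan describes the reactions that matter most to a safety study.

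**Working it through.** The plan states no figure to reproduce, and section 5.1 says that no sample size was calculated. The check compares the passages and needs one line of arithmetic.

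**Step 1: is an early record scheduled?**

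- Section 1.8: removal and washing for any discomfort; no record or contact attached.
- Section 2.8: GP contact for persistent irritation; no record attached. The same section says the study will not inform GPs, and section 1.6 says medical records will not be accessed, so a GP visit does not itself feed back to the study.
- Section 2.10.2 (Compliance): covers the timing of follow-up and loss to follow-up; it does not ask for time of removal.
- Table 1: no entry between Day 0 and Day 2.

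No section schedules an image, a symptom record or a removal time when a plaster comes off early.

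**Step 2: the gap between end of exposure and image.** Let t be the hour of removal and C the hour of the follow-up contact, with C at least 48.

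- Early remover: gap = C − t
- Full wear to hour 48: gap = C − 48
- Difference: (C − t) − (C − 48) = 48 − t, whatever the value of C

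The removal times below are assumptions, with C = 48.

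| Removal at hour t | Gap to image (48 − t) |
|---|---|
| 6 | 42 h |
| 8 | 40 h |
| 12 | 36 h |
| 24 | 24 h |
| 36 | 12 h |
| 48 | 0 h |

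Section 2.10.2 allows up to ten days before a volunteer is counted as lost. If that is counted from application (an assumption), C can reach 10 × 24 = 240. Removal at hour 12 then gives 240 − 12 = 228 h, against 240 − 48 = 192 h for full wear. The difference is still 36 h.

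**Step 3: which part of the outcome is exposed?**

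- *Frequency:* section 2.2 has volunteers asked about any sign of reaction, and section 3.3.1 covers symptoms within the 48 hours. A volunteer who stopped early can still be counted. No section makes a photograph a condition for counting.
- *Character and spread:* an image taken 48 − t hours after removal may no longer show the reaction. What remains is the volunteer's account.

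**Step 4: how many volunteers?** The protocol gives neither the proportion expected to remove early nor the time a reaction takes to fade. The number affected among the planned 90 to 100 cannot be computed.

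**The case against.** The strongest reply is that the protocol already has the parts it needs. Every volunteer receives an email address and a telephone number for immediate use. Section 1.5 promises an image of any suspected reaction without a time limit, and consent to hold images is an entry condition (section 2.5.1, criterion 8). Table 1 lists scheduled contacts and does not forbid an earlier image. The participant information sheet and the CRF, which are not shown, may carry the link.

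Much of this stands, and it rules out several stronger readings:

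- *Early stoppers leave without telling the study, or their reports arrive late.* A reader might infer this from section 1.8 alone. Section 1.6 offers an immediate route, so late reporting is possible but not built in.
- *Sections 1.6, 1.8 and 2.8 contradict one another.* A volunteer can follow them in sequence: contact the team, remove and wash, see a GP if symptoms persist. They are unlinked, not incompatible.
- *The frequency of reactions is understated.* It is obtained by asking, so a faded reaction can still be reported.
- *The halt decision in the first 10 is defeated.* Sections 2.8 and 5.2.2 hold back the remaining volunteers until the first phase has completed follow-up. Any delay would concern only first-phase volunteers still wearing plasters, and it depends on staggering that is not specified.

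What does not stand is that these parts close the gap. Section 1.6 offers contact for advice; it does not ask for a report on removal. The self-report sentence in section 3.3.1 concerns unexpected events, whereas redness, itchiness and discomfort, the likely reasons for removal, are listed there as expected. Where the protocol does give a time for the image, in sections 1.6 and 2.2 and Table 1, it is always at or after 48 hours. That contact can slip for anyone does not help either, since the difference of 48 − t remains.

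**Conclusion.** The point holds for the character and spread of reactions in volunteers who remove the plaster early. Under the schedule as written, their visual record comes 48 − t hours later after the end of exposure than it does in volunteers who wear the plaster for 48 hours and are contacted at the same hour. It may therefore have to be replaced by recall. Character is part of the primary outcome, and spread is among the features to be recorded.

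The conclusion assumes that some volunteers will act on the removal advice before 48 hours and that some reactions change visibly in the meantime. The protocol foresees the first and is silent on the second. It does not support a claim that the reaction rate will be biased or that the study will not hear of early reactions, and it gives no basis for a count of affected volunteers. This is a change the sponsor should make because it replaces a calendar rule that serves early reactors worse than completers. The trial does not fail without it.

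**What to change.** 1. Reconcile sections 1.6, 1.8 and 2.8 so that early removal is expressly linked to notifying the study through the existing email address or telephone number, and use the same wording in the participant information sheet.
2. Add an unscheduled early-removal entry to Table 1 and the CRF that records time of onset, time of removal, symptoms, and an image of the site sent by the volunteer at removal. Taking the image should not delay anything the volunteer has been advised to do.
3. Keep the 48-hour contact for everyone, so that early stoppers have both records.
4. In the report, give the time from removal to image alongside type and spread.

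The cost is small: protocol and information-sheet wording, one CRF page, and a few unscheduled contacts to log. The email account, the telephone line, volunteer-sent images and consent to hold images are already in the plan. The clinical content of the removal, washing and GP advice is left to the sponsor.

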## **2. TRIAL DESIGN**

### **2.1 Pilot trial**

Non-randomised, uncontrolled, Phase I pilot trial.

### **2.2 Trial summary**

Trial overview: Healthy volunteers will be sought by the research team using multiple strategies, including email circular invitations, social media and advertising the study to University of Warwick staff and students during academic term time. We will also seek a broad range of volunteers and will also recruit from the local community via groups (e.g. Women's Institute, activity groups) who have learned of the study via the media or our outreach activities (e.g. FH invited talks planned for January 2021). We will only recruit volunteers who are based in the surrounding locality (Coventry, Leamington, Warwick and Kenilworth). We aim to recruit between 90 to 100 volunteers in total.

After consent and recruitment, a small drop of the Bald's salve (intervention) will be applied onto a sticking plaster and applied to the participant's upper arm.

A fresh batch of the salve will be prepared using garlic and onions sourced from a commercial greengrocer, Pennard Organic white wine sourced from Avalon Vineyard, Somerset, and bovine bile (Merck Millipore catalogue no. B3883 suspended in sterile water). The salve will be passed through a 0.2µm syringe filter prior to use in this study to ensure sterility.

Outcomes will be captured at 48 hours. Due to Covid-19, face to face assessment of all participants will not be undertaken; this will be replaced with telephone or video contact supplemented with email.

Thus, after 48 hours, the participant will be contacted by the research team and asked to report any sign of skin reaction. We will ask participants to send a photographic image of the affected area. Some participants may be contacted by video (MS Teams, Zoom, Google or other video platform at the participant's discretion) for visual assessment of the affected area. We will collect and store photographs only from those reporting signs of redness or irritation and from a small sample of people with no symptoms (n=5), for comparison purposes.

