## STUDY SUMMARY

Trial Title	Assessment of safety of a medieval antibiotic to treat infected diabetic ulcers: a Phase 1 trial in healthy volunteers
Sponsor ref. number	
Clinical Phase	Phase I
Trial Design	Single centre non-randomised, uncontrolled intervention study
Trial Participants	Healthy volunteers, aged from 18 to 79 years
Planned sample size	100 participants
Treatment Duration	48 hours
Follow-up Duration	48 hours
Planned Trial Period	1 April 2021 to 1 July 2021 (3 months)
Objectives	
To aim is to determine the safety of an ‘ancientbiotic’ (Bald’s salve) when applied to the skin of human volunteers. The ancientbiotic is a mixture of natural products used in a historical infection remedy.
 
The specific objective is to determine the frequency of adverse events associated with a patch test of Bald’s salve applied to the skin of human volunteers.

Outcomes	
Primary	Skin irritation assessed at 48 hours.
Secondary	Any other adverse event associated with the patch test application of Bald’s salve.

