## **2.4 Outcome measures**

### **2.4.1 Safety profile of ancientbiotic**

#### **Primary Outcome:**

Frequency (prevalence) and character of adverse events at 48 hours after application of 100 µl ancientbiotic on a sticking plaster applied to the upper arm.

**Follow-up:** No further follow-up beyond 48 hours. If there is no skin reaction within 48 hours, we do not anticipate any longer term adverse events. However the study email account will be kept open for up to three months and participants will be advised to contact us if any suspected later reaction occurs.

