### **2.10.2 Compliance**

Follow-up will be after 48 hours. Anyone who we fail to contact after a maximum of ten days will be recorded as a loss to follow-up.

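### The outcome reading has no common time relative to plaster removal, so short-lived redness on removal may be counted in some volunteers and missed in others

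*Protocol*

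**What the plan says.** Section 1.5 describes a plaster "applied to the skin of the upper arm, worn for 48 hours". The outcome carries the same time. The Study Summary gives "Skin irritation assessed at 48 hours", section 2.4.1 counts "adverse events at 48 hours after application of 100 µl ancientbiotic on a sticking plaster applied to the upper arm", and section 2.2 adds "Outcomes will be captured at 48 hours".

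The reading is no longer made by staff at a visit. Section 1.8 reports: "Face to face assessment at 48 hours, as originally planned, has been replaced with telephone or video link contact". Section 2.2 then describes the contact: "after 48 hours, the participant will be contacted by the research team and asked to report any sign of skin reaction". No later reading is scheduled (section 2.4.1: "No further follow-up beyond 48 hours"), although an email account stays open for volunteers who notice something later. Section 2.9.2 provides reminders when there is no contact after 48 hours, and section 2.10.2 sets the outer limit: "Anyone who we fail to contact after a maximum of ten days will be recorded as a loss to follow-up".

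On removal, section 1.8 tells volunteers with discomfort to take the plaster off and wash the area. The protocol gives no routine removal step at the end of wear and no interval between removal and inspection. Table 1 still heads the Day 2 column as a clinic visit.

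**The concern.** Redness is the first sign named in the primary outcome (sections 1.5 and 5.1). Section 1.8 says that redness or irritation may come from the salve or from the plaster. If a plaster leaves redness that soon fades, whether it is counted depends on when the volunteer looks. One may look straight after removal, another some hours later, and a third may answer a reminder days later from memory.

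Nothing else in the design separates the two sources. There is no comparator arm (section 2.9.1), causality grading is set out for serious events only (section 3.4), and the five symptom-free volunteers photographed for comparison have also worn the salve. The reported frequency therefore depends partly on contact timing. At stake is a single uncontrolled proportion, set against a hypothesis of no irritation or inflammation (section 1.4). A reading time that was neither fixed nor recorded cannot be recovered after data collection.

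**Working it through.** The protocol states no power or sample-size figure to reproduce (section 5.1 says none was calculated). The check is of timing, followed by an illustration.

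**1. Nominal gap from end of wear to reading**
- Wear: 48 hours (section 1.5; the Study Summary also gives a 48-hour treatment duration).
- Reading: 48 hours after application (section 2.4.1).
- Gap: 48 − 48 = 0 hours.

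The Study Summary also lists a follow-up duration of 48 hours. Read as a second, consecutive period, this would suggest a later reading. Section 2.4.1 rules that out: it dates the outcome from application and ends follow-up at the same point.

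**2. Gap that the protocol allows**
- Contact is made after 48 hours (section 2.2), with a ten-day limit (section 2.10.2).
- If the ten days run from application: 10 − 2 = 8 days after the end of wear.
- If they run from the 48-hour point: 10 days.

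The time from removal to report can thus lie anywhere from about zero to 8 or 10 days. When the skin was inspected within that span is neither fixed nor recorded.

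**3. Illustration of size (assumed rates)**

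Let q be the proportion with short-lived redness from the plaster alone, f the fraction of those who look while it is visible, s the proportion with a salve reaction, and n the number of volunteers (90 to 100, section 2.2). The documents give none of q, f or s.

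Extra reactors counted when s = 0: n × q × f. The ceiling is f = 1, where everyone looks at once; the floor is f = 0.

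| Assumed q | Ceiling, n = 90 | Ceiling, n = 100 | Observed rate if s = 5%, f = 1: 1 − (1 − q)(1 − s) |
|---|---|---|---|
| 2% | 1.8 | 2 | 6.9% |
| 5% | 4.5 | 5 | 9.75% |
| 10% | 9 | 10 | 14.5% |
| 20% | 18 | 20 | 24% |

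The last column assumes that the two kinds of redness occur independently. With f below 1 the extra counts shrink in proportion.

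**4. Why a small q would still show**
- No events in 100: exact 95% upper limit 1 − 0.025^(1/100) = 3.6%. In 90: 1 − 0.025^(1/90) = 4.0%.
- Two events in 100: exact 95% interval 0.2% to 7.0%.
- Chance of at least one counted event from q = 2%, f = 1, s = 0: 1 − 0.98^100 = 0.87 in 100, and 1 − 0.98^90 = 0.84 in 90.

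Two volunteers with plaster redness only would move the upper limit from 3.6% to 7.0%.

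**The case against.** A reader might infer that every reading falls at the moment the plaster comes off. The documents do not say so. The coincidence is inferred from two 48-hour times, while section 2.2 speaks of contact after 48 hours and section 2.10.2 allows ten days. What is supported is that the interval is not fixed.

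A reader might also infer that some volunteers report on skin still under the plaster. That is speculative. Asking for signs and a photograph, or assessing by video, presupposes uncovered skin, and the participant information sheet and case report forms, which are not shown, may carry a removal instruction. They would not change the fact that the protocol defines the outcome without a reading time relative to removal.

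The outcome is not only a spot reading. Sections 1.5 and 5.1 count skin effects over the 48 hours, and section 3.3.1 captures symptoms during the period as well as at its end. This stands: a rule counting only what is present at one fixed look would drop reactions that came and went during wear, which a safety study should not do.

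The objective concerns adverse events associated with the patch test, and the adverse event definition does not require causation. So redness from the plaster is not formally declared a salve reaction, and people with known plaster allergy are excluded. This also stands in part, but the hypothesis in section 1.4 is about the product itself. A fixed interval would not separate lasting plaster irritation from salve irritation, nor a brief true reaction from redness on peeling. The lack of a comparator is a separate limit that this change does not cure.

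**Conclusion.** The point holds as a measurement weakness. Wear ends at 48 hours, the outcome is captured by remote self-report at or after that time, contact can run to ten days, and no common reading time relative to removal is set. Because the protocol itself names the plaster as a source of redness and has no comparator, the reported frequency can depend on when each volunteer looks.

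The size is unknown. The figures above rest on assumed rates and, at f = 1, on everyone looking immediately; they are ceilings. A reader might take 5 to 20 false reactors per 100 as an estimate. The documents do not support that, since they give no rate of plaster redness and no duration for it, and their own contact window means that only some volunteers would look at once. The firm conclusion is that readings will not be comparable across volunteers and that this is cheap to correct before recruitment.

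**What to change.** In section 2.2 and Table 1, state that at the end of the protocol's own 48-hour wear the volunteer removes the plaster, then inspects the site at one fixed interval after removal, the same for everyone and chosen by the trial team, before giving the outcome report. Where the protocol asks for a photograph, it is taken at that inspection. Record the times of removal and inspection on the case report form. The existing advice on discomfort is untouched; the recorded times show which volunteers removed the plaster early.

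Keep the primary outcome as all skin effects arising during the 48 hours or present at their end, and report within it:
- (a) effects present at the fixed reading;
- (b) effects noticed during wear;
- (c) redness seen only on peeling and gone by the reading.

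No safety event is dropped, and the reader can see how much of the total is short-lived redness on removal.

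The cost is one more instruction line, added fields on the case report form, and a brief wait for volunteers before they report.

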## **5 STATISTICAL ANALYSIS**

### **5.1 Power and sample size**

No sample size was calculated for this phase 1 study. The aim is to assess safety of the salve. The primary outcome will be adverse skin effects over 48 hours e.g. redness, heat, swelling or other. Type, number (%) and spread/distribution will be recorded.

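### The 48-hour question described asks for a sign of skin reaction, although itch and discomfort are expected events, so symptom-only reactions can be under-elicited or counted inconsistently

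*Protocol*

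**What the plan says.** **The question.** Section 2.2 describes the 48-hour contact in one sentence: "the participant will be contacted by the research team and asked to report any sign of skin reaction". A photograph of the area follows, and for some volunteers a video call. Section 1.8 explains that the face-to-face assessment first planned has given way to remote contact because of Covid-19.

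**The expected events.** Section 3.3.1 lists redness, "Skin itchiness" and discomfort as reactions that the salve may cause. It then commits the trial to symptoms: "We will capture symptoms arising within and at 48 hours".

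**The outcome.** The primary outcome is worded in several ways:
- Section 5.1: "The primary outcome will be adverse skin effects over 48 hours e.g. redness, heat, swelling or other". Section 1.5 gives the same examples: "Adverse skin effects over 48 hours e.g. redness, heat, swelling or other".
- Section 2.4.1: "Frequency (prevalence) and character of adverse events at 48 hours after application of 100 µl ancientbiotic".
- Study summary: "Skin irritation assessed at 48 hours" as primary, with a separate secondary outcome, "Any other adverse event associated with the patch test application of Bald’s salve".

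**The concern.** With no routine examination by the team at 48 hours, what the volunteer answers is the main source of the primary outcome, so the question works as the measuring instrument. A volunteer whose arm itched or stung under the plaster but looks normal could truthfully answer that there is no sign of a reaction, and would have nothing to photograph. Two of the three reactions that the protocol itself expects are of this kind, and neither is among the named examples in the outcome.

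There is also a counting question. If such a volunteer does mention the itch, the protocol does not settle whether it enters the primary frequency or the count of other adverse events.

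The frequency and character of adverse events is the sole objective (2.3.1), and the hypothesis (1.4) is that there will be no irritation or inflammation. Any reaction that is not elicited or not counted moves the result towards that hypothesis, and there is no comparator arm in which the loss would show.

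**Working it through.** The protocol states that no sample size was calculated and gives no expected frequency, so there is no figure of its own to reproduce. The check is a comparison of the sections, followed by the arithmetic of one uncounted reaction.

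**1. The two lists side by side**

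| Effect | Outcome examples (1.5, 5.1) | Expected events (3.3.1) |
|---|---|---|
| Redness | named | named |
| Heat | named | not named |
| Swelling | named | not named |
| Itchiness | only through the catch-all | named |
| Discomfort | only through the catch-all | named |

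Only redness is on both lists. Itchiness and discomfort are the two that can occur with nothing to see.

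**2. Where itch without visible change would be counted**

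- Section 2.4.1: primary, because all adverse events count and 3.3.1 names itch as one.
- Sections 1.5 and 5.1: primary, but only through the catch-all.
- Study summary: arguable. It is primary if read as skin irritation, secondary if read as another adverse event.

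Two assessors following the protocol could therefore place the same volunteer differently.

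**3. How it would be elicited**

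The sentence in 2.2 is the only 48-hour question described. Section 3.3.1 promises to capture symptoms but does not say how. Its sentence on self-report concerns unexpected events, whereas itch and discomfort are listed as expected. Contact may be by phone or email (1.6), by telephone or video with email in support (2.2), or by postal form with telephone completion (2.9.2). No common item wording is set across these modes.

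**4. Size per uncounted reaction**

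With *N* volunteers, the frequency is the number of reactors divided by *N*, so one uncounted reactor lowers it by 1/*N*. Section 2.2 plans 90 to 100 volunteers:

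- *N* = 100: 1/100 = 1.0 percentage point.
- *N* = 90: 1/90 = 1.1 percentage points.

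**5. Illustration (the number of symptom-only reactors, *k*, is assumed)**

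Suppose no visible reactions and *k* symptom-only reactors. Exact (Clopper-Pearson) 95% limits are the 0.025 quantile of Beta(*k*, *N* − *k* + 1) and the 0.975 quantile of Beta(*k* + 1, *N* − *k*), with a lower limit of 0 when *k* = 0.

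| *k* counted | *N* = 100 | *N* = 90 |
|---|---|---|
| 0 | 0% (0 to 3.6) | 0% (0 to 4.0) |
| 2 | 2.0% (0.2 to 7.0) | 2.2% (0.3 to 7.8) |
| 5 | 5.0% (1.6 to 11.3) | 5.6% (1.8 to 12.5) |
| 10 | 10.0% (4.9 to 17.6) | 11.1% (5.5 to 19.5) |

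If all *k* went uncounted, the first row would be reported in place of the later one. The table shows what is at stake for a given *k*. It does not predict *k*.

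**The case against.** The case on the other side is substantial, and most of it stands.

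- **Both lists are open.** The outcome list is introduced as examples and ends in a catch-all, and the expected list says only what events may include. Different examples in two open lists are not a contradiction.
- **Section 2.4.1 already covers symptoms.** It counts adverse events, and 3.3.1 names itch and discomfort among them.
- **There are other routes of capture.** Besides the promise in 3.3.1, Table 1 has a Day 2 row for other adverse events, section 3.5 has co-investigators check for adverse events at follow-up, and section 1.6 gives volunteers contact details to use at once.
- **The word may be loose.** Section 2.2 is an overview, not interview wording, and the same section speaks of irritation and contrasts reactors with people who have no symptoms.
- **The case report form is not shown.** Section 4.1 says the forms have been developed, and they may already ask for symptoms item by item.

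A reader might infer that volunteers are asked about signs and nothing else, or that a swelling or heat reaction would have to be classed as unexpected. The documents support neither: the other routes of capture answer the first, and the open expected list answers the second.

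What the objection leaves is narrower. The one question described is worded around a sign while the protocol promises symptoms. The Day 2 row for other adverse events is separate from the outcome assessment, so recording itch there does not settle that it counts as primary. Section 2.4.1 and the study summary still leave room for different counts.

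**Conclusion.** The point holds as a weakness of elicitation and definition, not as an exclusion of symptoms. Reactions felt but not seen can be under-elicited by the question described, and can be counted as primary under 2.4.1 but arguably as secondary under the study summary.

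The firm size is the effect of each one left out: 1.0 percentage point at *N* = 100 and 1.1 at *N* = 90. It would also be tempting to conclude that the reported frequency is biased low, or to put a total on the loss. The documents do not support that: they give no expected frequency and no share of reactions that are symptoms only, and without the case report form nobody can say how many would be missed. The frequency can be biased low; whether it will be is unknown.

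The change is worth making because it improves the measurement of the trial's only endpoint at little cost, and because symptoms not asked about at 48 hours cannot be reliably recovered later.

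**What to change.** - **Section 2.2:** replace the open request with fixed yes/no items, asked of every volunteer in the same words whether by phone, video, email or post: redness, itchiness, discomfort, heat, swelling, other. Ask about any time within the 48 hours as well as at the 48-hour point.
- **Sections 2.4.1 and 5.1:** state that any yes, with or without a visible sign, is a primary event, and report the number (%) for each item. Bring the study summary and the examples in 1.5 and 3.3.1 into line with the same list and period.
- **Case report form:** check that it carries these items. If it already does, only the protocol wording needs to change.

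The cost is wording in the protocol and form, and about one more minute per contact. The downside is that prompting will raise the count of trivial complaints, so the overall frequency may look less favourable. Reporting by item keeps that visible, since a reader can separate itch alone from redness or swelling.
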